Despite these promising reports of long term survival among highly selected patients who undergo resection of pulmonary metastases from gastric cancer, metastasectomy has not been scientifically studied as a potential routine practice in the management of this disease. Furthermore, no studies have adequately addressed this topic in a prospective, randomized fashion comparing metastasectomy to best alternative care of systemic chemotherapy. While considering the retrospective nature, inherent biases and limited experience from these studies, clearly there is a potential group of highly selected patients that might benefit significantly from aggressive approach to pulmonary gastric metastases. This study is designed to answer the question: What are the characteristics of patients who might benefit from the GYMS approach for metastatic gastric cancer, including metastases to the lung.

The rational for using FOLFOXIRI in this trial:

Metastatic gastric cancer remains a therapeutic challenge due to poor prognosis and optimum chemotherapy regimen for this disease has not been established. Several randomized phase III trials comparing combination chemotherapy such as 5-fluorouracil (5-FU), doxorubicin, and mitomycin or 5-FU, doxorubicin and high dose methotrexate with best supportive care have demonstrated significantly prolonged overall survival (OS) of 8-10 months for chemotherapy group as compared with 3-5 months in the best supportive care alone group^{59,60}. Since then, various combination chemotherapy regimens were tested in phase II or phase III trials in metastatic gastric cancer without significant improvement in overall survival. A recent phase III trial comparing docetaxel-cisplatin-5-FU (DCF) to the reference arm of cisplatin-5FU (CF) showed a modest improvement in OS (9.2 vs. 8.6 months), time to progression (5.6 vs. 3.7 months), and response rate (37% vs. 25%) for the DCF arm⁶¹. These results represent one of the best improvements in treatment of metastatic gastric cancer. However, DCF was associated with high rates of grade 3 and 4 toxicities, and as a consequence the regimen has not yet been widely accepted.

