Irinotecan, a camptothecin analog, acts as an anti-tumor agent by inhibiting the eukaryotic enzyme DNA topoisomerase I. Irinotecan has demonstrated high activity as a monotherapy in gastric cancer patients with response rates from 18% to 43%^{62,63}. Phase II studies with irinotecan plus 5-FU and leucovorin (FOLFIRI) showed a response rate of 40% with median survival time between 10.7 and 12.6 months⁶⁴⁻⁶⁶. A phase II study of modified FOLFIRI in gastric cancer patients who had failed taxane/cisplatin chemotherapy reported a response rate of 21% with low toxicity profile⁶⁷.

Oxaliplatin, an alkylating agent, inhibits DNA replication by forming DNA adducts between two adjacent guanines or guanine and adenine molecules. Oxaliplatin has shown a notable activity against colorectal cancer in combination with 5-FU and leucovorin, which has led to several phase II trials in gastric cancer. The oxaliplatin/5-FU/leucovorin regimen yielded response rates in the range of 38% to 54% with a survival time from 8 to 11 months with favorable toxicity profile⁶⁸.

In an attempt to develop a more active and efficacious chemotherapy regimen, irinotecan and oxaliplatin, have been combined with or without 5-FU and leucovorin in a few phase I trials, which have shown safe toxicity profiles in patients with advanced solid tumors⁶⁹. Preclinical studies reported synergistic anti-tumor activities between irinotecan and oxaliplatin in several tumor cell lines⁷⁰. A phase II study of irinotecan, oxaliplatin plus continuous infusion of 5-FU/leucovorin without chronomodulation in 32 colorectal cancer patients produced very promising activity with a response rate of 72%⁷¹. Another phase II study of FOLFIRINOX in advanced pancreatic cancer patients also yielded response rate of 26% with manageable toxicity⁷².

On the basis of these encouraging results, several phase II studies were recently executed in order to assess the efficacy and safety of the modified FOLFOXIRI as a frontline chemotherapy in patients with metastatic gastric cancer^{73,74}. Results from these trials are among the best ever reported in gastric cancer: Overall response rate of 63-66%

(CR 2-4% and PR 60-65%), median survival 12-15 months, and median time to progression 7-10 months. The most common grade 3/4 toxicities were: neutropenia (12-49% of all cycles), emesis (8-42% of all cycles), grade 2 neuropathy (10%), grade 3 diarrhea (10%), and stomatitis (4%). No grade 4 non-hematologic toxicities were observed.

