3.5.2. Treatment Schedule FOLFOXIRI

[figure not shown]
Systemic chemotherapy will be administered every other week (one treatment every 14 days), and repeated for 12 cycles (approximately 6 months). Patients in the systemic chemotherapy alone (SA) arm who are responding may continue chemotherapy beyond 12 cycles at the discretion of the PI. Refer to Section 8 for further administration guidelines.

Day 1: Irinotecan will be administered IV over 90 minutes followed by leucovorin IV and oxaliplatin IV given concomitantly over 2 hours, followed by 5-FU given via continuous infusion (CIV) over 48 hours.

Dose Level

Agent	Starting Dose	Dose level -1 (25% reduction)	Dose level -2 (50% reduction)
Irinotecan	165mg/ m ² IV	123 / m ² IV	82 /m ² IV
Leucovorin	200 mg/m ² IV	200 m ² IV	200 mg/m ² IV
Oxaliplatin	85 mg/m ² IV	63 mg/m ² IV	42 mg/m ² IV
5-FU	3200 mg/m ² CIV	2400 mg/m ² CIV	1600 mg/m ² CIV

Cycle 1 Week 1

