3.8. Off Treatment Criteria

- Completion of systemic chemotherapy regimen
- Voluntary withdrawal from treatment
- Inability to follow the treatment regimen
- Unacceptable toxicity
- Radiographic or clinical disease progression
- Unwilling or unable to undergo surgical resection for progressive disease
- If the physician deems it is in the patient's best interest not to receive further treatment
- Completion of chemotherapy

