3.10. Off Study Criteria

- Death

- Unwillingness to participate in study specified follow up (including phone contact)
- If the physician deems it is no longer in the best interest of the patient to remain on study

Note: As the objective of this study is overall survival, every attempt will be made to follow patients for life.

Patients will be officially taken off study by contacting the CRO.

3.11.Measurement of Health Related Quality of Life

Baseline Quality of Life Questionnaires (QOL) will be completed prior to randomization, prior to cycle 9 of chemotherapy and then every 12 weeks (+/- 2 weeks) for the first 2 years, every 6 months for the next 3 years, and yearly thereafter. (Note: patients who begin chemotherapy >5 weeks following randomization will be asked to complete the QOL prior to the first cycle of chemotherapy.

Patients will be informed of the details of the QOL part of this study and reassured that their decision to participate will not affect their participation in the either of the treatment arms of this protocol. Once enrolled, the patient has the right at any time to elect not to continue completing the questionnaires. In the event a patient goes off study prior to completion of the follow up time points, the data gathered from their completed QOL questionnaires will be included in the final analysis.

To QOL parameters and quality of life adjusted survival between the two study groups, we will use tools specifically developed for assessment of QOL in gastric cancer patients: FACT-Ga, ; Blazeby JM, Eur J cancer 2004 (Appendix 6). Measures will be initially administered by the Associate Investigator Research Nurse or designee prior to randomization. The Research Nurse will assess the patient's ability to read, and if the patient is unable to read, it will not be administered. The Research Nurse or designee will administer the questionnaires providing a firm surface at a table or a clipboard and a pencil. The patients will be directed to complete the questionnaires using the following instructions:

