The evaluation for better than expected efficacy will be performed as follows. Beginning at the first annual DSMB meeting after 68 patients have been randomized, annual interim evaluations will be performed to determine if there is sufficient evidence to terminate accrual because of a better than expected improvement in overall survival. An alpha spending function approach to monitoring will take place using an O'Brien-Fleming interim evaluation boundary ⁷⁹. It will be assumed that a total of 121 deaths would take place over a total of 8 years of accrual plus monitoring, and that monitoring would begin after approximately 40-45 deaths have been noted. The information fraction used to compute the interim boundary at each annual evaluation will be calculated as the number of patients who died /121.

Quality of life evaluations will be compared between the two study arms, with comparisons at multiple individual time points, as well as with respect to changes from baseline. Wilcoxon rank sum tests will likely be used. The evaluation will be considered secondary, and p-values resulting from the analysis will be presented without adjustment for multiple comparisons, but in the context of the number of tests evaluated.

It is expected that 24 patients per year can be accrued onto this trial, and thus accrual will be completed in approximately 6 years. Allowing for a very small number of inevaluable patients, the accrual ceiling will be set at 140 patients.

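### The quality-of-life form tied to chemotherapy cycle 9 misses patients who stop early and falls at different times in the two arms

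*Combined protocol and SAP*

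**What the plan says.** Section 3.11 sets the quality-of-life calendar. After a baseline form before randomization, forms are due "prior to cycle 9 of chemotherapy and then every 12 weeks (+/- 2 weeks) for the first 2 years", and less often after that. There is one supplement: "patients who begin chemotherapy >5 weeks following randomization will be asked to complete the QOL prior to the first cycle of chemotherapy". In practice these late starters are GYMS patients and any SA patients who have a palliative gastrectomy.

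Section 3.5.2 plans 12 cycles of 14 days. Sections 3.5.3 and 3.8 end chemotherapy for toxicity, withdrawal or progression; the list in 3.8 includes "Radiographic or clinical disease progression". Section 3.1.2 takes GYMS patients off treatment if they have not recovered within 16 weeks of surgery, with a longer limit after thoracotomy.

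Section 5.4 compares the arms "with comparisons at multiple individual time points, as well as with respect to changes from baseline", probably by Wilcoxon rank sum tests. It gives no rule for missing forms and does not say who is included at each time point.

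**The concern.** Reaching cycle 9 is an outcome of treatment. A form that exists only for patients who reach it defines a subset after randomization. In both arms the subset is filtered by tolerance and freedom from progression, and in GYMS also by recovery from surgery. The comparison at that time point is then no longer between the randomized groups. Because the form follows the chemotherapy calendar, it also reaches the two arms at different distances from randomization.

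Comparing quality of life is a stated secondary objective (Section 1.1.2), and Section 3.11 also mentions quality-adjusted survival, which needs scores after treatment has failed or stopped. In a trial of major surgery plus chemotherapy against chemotherapy alone, patients who do not recover or who stop early may carry much of the quality-of-life cost. They are the patients with no form here.

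**Working it through.** **Plan's own figures.** The documents state no expected completion rate for the forms. The survival model in Section 5.4 does reproduce: ln2/12 = 0.0578 and ln2/20 = 0.0347 per month, giving 12-month survival of 50% and 66%. The same exponential model is used below, with 1 month = 30.4375 days.

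**1. When the form falls.** Cycle 9 opens 8 × 14 = 112 days, or 16 weeks, after the first dose. The next form, 12 weeks later, is at week 28, after a course of about 24 weeks. The cycle 9 form is therefore the only one inside the planned 12 cycles.
- SA: start by week 2 (Section 3.5.1), so 2 + 16 = week 18.
- GYMS: surgery at 1-2 weeks (3.1.2) and chemotherapy about 6-8 weeks later (3.5.1), so 1 + 6 + 16 = 23 to 2 + 8 + 16 = 26 weeks.
- GYMS with slow recovery, up to the 16-week limit in 3.1.2: 2 + 16 + 16 = week 34. With sequential thoracic surgery, starting by week 24 (3.2.8): 24 + 16 = week 40.

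**2. Share of SA progressed or dead by week 18.** Section 1.2 cites "median time to progression 7-10 months" for the study regimen. Week 18 is 126/30.4375 = 4.14 months, and the share is 1 − exp(−ln2 × t/median).
- Median 10 months: 24.9%.
- Median 7 months: 33.6%.

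**3. Deaths by the same date.** With the 12-month planning median for SA, 1 − exp(−ln2 × 4.14/12) = 21.3%. No schedule can collect forms from these patients.

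**4. Living SA patients lost through progression**, as a share of those randomized:
- If the progression figure includes deaths: 24.9 − 21.3 = 3.6% to 33.6 − 21.3 = 12.3%, or roughly 4-12% (about 3 to 8 of 68).
- If progression and death are independent: 0.787 × 24.9% = 20% to 0.787 × 33.6% = 26% (about 13 to 18 of 68).

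Patients stopping for toxicity or withdrawal add to this. The documents give no rate for them.

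**5. GYMS.** No progression time after resection is given, so any figure is an assumption. On the same 7-10 month medians, 31-41% have progressed by week 23 and 34-45% by week 26. If the planned survival hazard ratio of 0.6 also applied to progression (medians 11.7 and 16.7 months), the share at week 26 is 22-30%. Deaths by week 26 under the 20-month median are 1 − exp(−ln2 × 5.98/20) = 18.7%, so these figures also include patients who could not be assessed.

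**6. Sensitivity to shape.** Counted from first dose (3.68 months), the exponential model gives 22.5-30.5%. A Weibull shape of 1.5 gives 14-23%, and a shape of 0.8 gives 27-34%.

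**The case against.** The strongest reply is that this is one time point among many in an unadjusted secondary analysis, and that patients who stop are not lost to quality-of-life follow-up. Section 3.9 requires forms at 12-weekly post-treatment visits. Section 3.11 mails forms every 6-12 months to patients followed only for survival, asks for a last set when a patient goes off study, and keeps partial data. All of this stands, and it rules out reading the point as a loss of all quality-of-life data. It does not fill the gap: none of these contacts is aligned to the cycle 9 form, and coming off treatment does not trigger the last set, because progression is not an off-study criterion in Section 3.10.

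Four stronger readings are tempting, and the documents do not support them.
- *That the 25-34% are all living patients whose forms could be recovered.* The plan's own hazard puts about 21% of SA dead by week 18. Treating the whole share as missing forms, or computing a loss of precision from it, charges mortality to the schedule.
- *That the 12-weekly forms have no anchor for a patient without a cycle 9.* The design list in Section 3 dates all follow-up evaluations from randomization. Section 3.9 counts instead from the end of chemotherapy, so the two conflict, but an anchor exists.
- *That each arm's overstated mean is the bias in the comparison.* A deficit shared by both arms largely cancels. The documents give no score deficit for patients off treatment and no reason to assume it is equal in the two arms, so neither direction nor size can be stated.
- *That every progressor before cycle 9 misses the form.* Section 3.7 puts the second scan at about week 16 of chemotherapy, and Section 3.11 asks for forms before the physician is seen. Some patients found to have progressed on that scan may already have completed it. By the week 8 scan (1.84 months) the model gives 12-17%.

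The 7-10 month medians also come from first-line phase II studies, whereas this trial admits previously treated patients and resects one arm.

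**Conclusion.** The defect holds for one named comparison. As written, the cycle 9 comparison is restricted to patients still on chemotherapy and is made at about week 18 in SA against weeks 23-26 or later in GYMS. Under exponential times and the cited medians, living SA patients lost through progression are roughly 4-12% of those randomized if the progression figure includes deaths, and 20-26% if the two are independent, plus those stopping for other reasons. These shares fall if progression is slow at first or if the form is completed before the week 16 scan is read. The GYMS share is uncertain. The timing difference between arms follows from the schedule itself and needs no progression assumption. The effect on the between-arm difference is unknown in direction and size. It is a secondary-endpoint point, worth correcting because the correction is cheap.

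**What to change.** - **Section 3.11:** replace the cycle 9 form with one due at a fixed time from randomization for every living randomized patient, whether chemotherapy was started, continued or stopped. Use the existing mail and telephone route for patients not attending. That route names only the FACT-Ga, so say whether the other instruments are mailed too.
- **Sections 3.9 and 3.11:** run the 12-weekly forms from the randomization date, in line with the design list in Section 3, and reconcile Section 3.9, which counts from the end of chemotherapy.
- **Section 5.4:** state that each time-point comparison includes all randomized patients alive at that time.

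As an illustration, at week 16 only death would remove patients by design: 19% in SA and 12% in GYMS under the planning medians, leaving about 55 + 60 = 115 of 136 assessable.

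The cost is wording in these sections and some extra mailed forms, with no new instrument or visit. The downside is that the form no longer falls at the same chemotherapy cycle for every patient.

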3.1. Staging Laparoscopy

3.1.1. Patients who meet eligibility criteria will be taken to the operating room for staging laparoscopy and peritoneal washings. At laparoscopy biopsies of the peritoneum will be done and used later to confirm status of peritoneal disease (not as a part of the staging procedure but as part of the study).

- Any suspicious lesions that might preclude resection to NED will be biopsied as well.
- Liver ultrasound to confirm axial imaging findings will be done.
- Randomization and stratification will be done after laparoscopy and only after the results of the peritoneal washings are known (within one week of laparoscopy).

3.1.2. Patients will then be randomized to receive gastrectomy and/or metastasectomy plus systemic therapy (GYMS arm) or systemic therapy alone (SA arm).

- Patients randomized to receive the standard of care (SA arm) will receive systemic therapy (as described in Section 3.5). **Note:** Patients may undergo palliative gastrectomy if indicated but must begin chemotherapy within 6 weeks of gastrectomy (8 weeks following randomization).
- Patients randomized to receive gastrectomy and/or metastasectomy plus systemic therapy (GYMS arm) will be taken to the operating room within 1-2 weeks of randomization (as soon as feasible). Patients may undergo surgery only at the NCI. Subsequently, patients will receive systemic therapy within 4 to 16 weeks after surgery and/or when fully recovered from surgery. Patients who do not recover within 16 weeks will be taken off treatment and followed for survival. (**Note:** patients who undergo thoracotomy for pulmonary metastases must be able to receive systemic therapy within 24 weeks of their initial surgery.) This is an intent-to-treat phase III trial.

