3.4.4. Post Discharge

- Patients will have CBC with differential and Chem 20 drawn weekly until values are less than or equal to grade 2 or baseline. This may be done through the patient's referring physician with the results faxed to [name] or his designee.

- Patients will return to clinic approximately 4-6 weeks following surgery for their 1st post operative visit. Subsequent follow up is detailed in section 3.9.

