3.5. Systemic Chemotherapy Therapy

3.5.1. Guidelines

Patients who randomize to receive systemic chemotherapy alone (SA) will begin treatment within 14 days of randomization; patients who undergo palliative gastrectomy will begin chemotherapy within 6-8 weeks of randomization. Patients who randomize to surgery plus chemotherapy (GYMS) will begin treatment approximately 6-8 weeks following surgery (24 weeks for patients requiring sequential thoracic and abdominal surgery). **Note:** patients must meet eligibility requirements prior to beginning chemotherapy. Patients who do not recover from the surgical procedure within the stated timeframe will be removed from treatment and followed for survival.

Systemic therapy may be administered by the patient's local oncologist in collaboration with the PI or at the NCI by the Medical Oncology Branch. Systemic therapy will follow the guidelines for the FOLFOXIRI regimen⁷⁷. Chemotherapy and supportive care will be administered in accordance with each institution's policies for the administration of chemotherapeutic agents.

During treatment, the treating oncologist will be asked to fax the following information (Appendix 8) to the research nurse (noted below) at the conclusion of every other cycle (4 weeks):

- chemotherapy administration sheets including dose reductions and reason for dose reduction
- laboratory test results
- other clinically relevant information

The patient will be asked to maintain a diary to be faxed to the research nurse every 4 weeks:

[name] RN
[contact]

All systemic chemotherapy will be administered based on actual body weight if within 20% above or below the ideal body weight. If actual weight is not within 20% of ideal body weight, then ideal body weight will be used to calculate systemic chemotherapy doses.

Ideal body weight will be calculated based upon the following formula:

$$\begin{aligned} \text{IBW (male, in kg)} &= \{(\text{Height in inches} - 60 \} \times 2.3 \} + 50 \\ \text{IBW (female, in kg)} &= \{(\text{Height in inches} - 60 \} \times 2.3 \} + 45.5 \end{aligned}$$

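### Section 3.11 gives the quality-of-life comparison no matched early time point: no form falls between surgery and chemotherapy in GYMS, and the GYMS pre-chemotherapy form has no counterpart in SA patients who start promptly

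*Combined protocol and SAP*

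**What the plan says.** Section 3.11 sets the schedule. The questionnaires "will be completed prior to randomization, prior to cycle 9 of chemotherapy and then every 12 weeks (+/- 2 weeks) for the first 2 years", then every 6 months for 3 years and yearly after that. A note adds that "patients who begin chemotherapy >5 weeks following randomization will be asked to complete the QOL prior to the first cycle of chemotherapy".

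The trigger for that extra form depends on when chemotherapy starts.

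- **GYMS.** Section 3.1.2 places surgery 1-2 weeks after randomization and then says "patients will receive systemic therapy within 4 to 16 weeks after surgery and/or when fully recovered from surgery". Section 3.5.1 instead gives about 6-8 weeks after surgery, with 24 weeks for sequential thoracic and abdominal operations. Patients who do not recover in time stop protocol treatment and are followed for survival.
- **SA.** Section 3.5.1 requires a start within 14 days of randomization, or at 6-8 weeks for patients who first have palliative gastrectomy.

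Section 3.4.4 provides a visit in the recovery period: "Patients will return to clinic approximately 4-6 weeks following surgery for their 1st post operative visit". It lists no quality-of-life form. Sections 3.4.1 to 3.4.3 list none in hospital or at discharge, section 3.7 only refers back to 3.11, and the section 3.9 visits follow completion of chemotherapy.

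Section 5.4 compares the arms "with comparisons at multiple individual time points, as well as with respect to changes from baseline", probably by Wilcoxon rank sum tests. It does not name the time points and gives no rule for forms that fall at different times in the two arms.

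**The concern.** Comparing quality of life between the arms is a secondary objective (section 1.1.2), and section 3.11 also mentions quality-adjusted survival. Both need some account of the first months, when one arm is recovering from major surgery and the other is on triplet chemotherapy.

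The schedule ties the only early form to starting chemotherapy late. This has two consequences. In GYMS, the form is completed only by patients well enough to start, so the early sample is defined by an outcome of the surgery. In SA, a patient who starts on time never triggers the form, so there is nothing concurrent to compare it with.

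Other records do little to fill the gap. Section 3.2 keeps perioperative detail off the case report forms. Section 7.3.2 leaves out of the database grade 2 events during the surgical admission and grade 3-4 events that resolve within 72 hours of surgery.

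**Working it through.** **Inputs.** Randomization to surgery: 1-2 weeks (3.1.2). Surgery to chemotherapy: 6-8 weeks (3.5.1) or 4-16 weeks (3.1.2). SA start: week 0-2, or week 6-8 after palliative gastrectomy (3.5.1). Cycle length: 14 days, 12 cycles (3.5.2). No cycle delays are assumed.

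**The plan's own figure.** 12 × 14 days = 168 days = 24 weeks. 168 / 30.4375 = 5.5 months, which agrees with the stated duration of approximately 6 months.

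**Formulas.** Week of cycle 1 (GYMS) = weeks to surgery + weeks from surgery to chemotherapy. Week of cycle 9 = week of cycle 1 + 8 × 2 = week of cycle 1 + 16.

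| Group | Cycle 1, week from randomization | Pre-cycle-1 form? | Cycle 9 form, week |
|---|---|---|---|
| SA, start within 14 days | 0-2 | no | 16-18 |
| SA, palliative gastrectomy | 6-8 | yes | 22-24 |
| GYMS, 3.5.1 | 1+6 = 7 to 2+8 = 10 | yes | 23-26 |
| GYMS, 3.1.2 | 1+4 = 5 to 2+16 = 18 | only if after week 5 | 21-34 |
| GYMS, sequential thoracic surgery (3.5.1) | up to 2+24 = 26 | yes, if after week 5 | up to 42 |

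**What follows.**

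1. No scheduled form falls between surgery at week 1-2 and readiness for chemotherapy. A GYMS patient who starts at exactly week 5 does not meet the more-than-5-weeks condition and has no form until about week 21.
2. The week 7-10 GYMS form has no concurrent form from an SA patient who started within 14 days.
3. The first form common to both arms, before cycle 9, is itself unmatched in calendar time. Under 3.5.1, GYMS is later by 23 − 18 = 5 to 26 − 16 = 10 weeks; under 3.1.2, by 21 − 18 = 3 to 34 − 16 = 18 weeks.
4. GYMS patients who do not recover never reach a pre-cycle-1 form. Section 3.11 gives patients followed only for survival mailed forms every 6-12 months. Its final set of forms is for patients taken off study, whereas failure to recover takes a patient off treatment.
5. The existing first post-operative visit falls at week 1+4 = 5 to 2+6 = 8, so a week-6 form fits within it.

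**SA patients lost before cycle 9 (illustration).** Progression ends treatment (3.8). The 16 weeks from cycle 1 to cycle 9 are 16 × 7 / 30.4375 = 3.68 months. Assume exponential times and the 7-10 month median time to progression that section 1.2 quotes from frontline phase II studies. Then 1 − exp(−ln2 × 3.68/7) = 31% and 1 − exp(−ln2 × 3.68/10) = 23% would progress before that form. This trial also admits previously treated patients, so the figures only illustrate the possible size.

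**The case against.** **The direction of bias.** A reader might infer that the schedule tilts the comparison towards GYMS, because it passes over the weeks when surgery costs most. The documents do not support that. The early FOLFOXIRI toxicity of SA patients who start promptly is also unmeasured. Section 1.2 reports grade 3/4 neutropenia in 12-49% and emesis in 8-42% of cycles. SA patients who progress before cycle 9 drop out of the on-treatment sample, which would flatter SA at that form. The effects run in both directions, and the net result is unknown.

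**Surgical loss is not wholly invisible.** A form 6-8 weeks after gastrectomy can still show a fall from baseline. Section 3.1.2 joins full recovery to the time window with and/or, so recovery is not a strict condition, and eligibility allows ECOG up to 2. This stands. What remains is that the form comes only from those who start chemotherapy and has no SA counterpart at that time, apart from palliative gastrectomy patients.

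**SA is not uniformly unmeasured before cycle 9.** Palliative gastrectomy patients do receive the pre-cycle-1 form, at week 6-8. This also stands, but they are a selected subgroup and cannot represent the arm.

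**Follow-up timed from randomization.** Section 3 says that follow-up evaluations are timed from randomization, which might suggest a week-12 form in both arms. Section 3.11 places the 12-weekly forms after cycle 9. Even a week-12 form would come after the usual week 7-10 chemotherapy start.

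**Scope.** Section 5.4 does not claim that the schedule is identical in the two arms, and a time point with no SA form cannot be tested between arms. That is fair, but it leaves the plan with no early comparison at all.

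**Conclusion.** The point holds as a gap in coverage and matching. From surgery at week 1-2 until chemotherapy begins, usually week 7-10 under section 3.5.1, no GYMS form is scheduled. The form that follows is selected on fitness for chemotherapy. SA patients starting within 14 days are not re-measured until week 16-18. The planned between-arm comparison therefore cannot describe the early course, and no direction of bias can be assigned.

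The week numbers assume that the protocol windows are met and no cycles are delayed. The 23-31% figure also rests on exponential progression and on medians from other studies. The conclusion does not depend on it.

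The matter concerns a secondary endpoint, whose p-values section 5.4 already presents without adjustment for multiple comparisons. The primary overall survival analysis is unaffected. It is a cheap and worthwhile improvement, since data from this period cannot be recovered later.

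**What to change.** - **Section 3.11:** add one form in both arms at about week 6 from randomization, completed whether or not chemotherapy has started. In GYMS, use the first post-operative visit (3.4.4). In SA, use the nearest two-weekly chemotherapy assessment (3.6).
- **Mail route:** extend it to patients treated by a home oncologist. As written, it covers only patients followed for survival and sends only the FACT-Ga, so the text must say which instruments are mailed at this time point.
- **Section 5.4:** name week 6 as the early between-arm comparison, and state that the GYMS pre-cycle-1 form is not used for a between-arm test. It can still be described within GYMS.
- **Chemotherapy start windows:** sections 3.1.2 (4-16 weeks after surgery) and 3.5.1 (about 6-8 weeks) differ and must be reconciled, because they determine when the pre-cycle-1 and cycle-9 forms fall. The same applies to the 24-week limit for thoracic cases, which 3.1.2 counts from the initial surgery and 3.2.8 from randomization.

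**Cost.** One extra set of forms per patient, which the section 3.11 script puts at no more than 15 minutes, plus protocol wording and some mailing and telephone follow-up. The new form will not capture the hospital stay of roughly 7-21 days (3.4.3), and it leaves the unequal calendar timing of the cycle-9 form as it is.
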